6.5.4 Guidelines for the management of specific adverse events

Specific adverse events described in sections below may classify as adverse events of special interest (AESIs), depending on grading according to National Cancer Institute- Common Terminology Criteria for Adverse Event (NCI-CTCAE) V5.0 (see Section 8.3.8 of the master protocol). In case a specific adverse event meets the AESI definition it must be documented in the e-CRF.

6.5.4.1 Infusion-related reactions (IRR)

Participants should routinely receive premedication as detailed in Section 6.1.2.1 of the master protocol prior to SAR444245 administration, to prevent or reduce the incidence or severity of IRRs.

An infusion-related reaction in this study is defined as any signs or symptoms which develop during the infusion or up to 24 hours after the completion of the infusion. The term IRR indicates only a specific temporal relationship with the infusion and does not specify a particular mechanism underlying the signs or symptoms.

Pembrolizumab may cause severe or life-threatening infusion-reactions including severe hypersensitivity or anaphylaxis. Signs and symptoms usually develop during or shortly after drug infusion and generally resolve completely within 24 hours of completion of infusion. Dose modification and toxicity management guidelines on pembrolizumab-associated infusion reaction are provided in [Table 3](#).

After an infusion-related reaction due to pembrolizumab infusion (Grade 3 or Grade 4), the SAR444245 infusion will be delayed and can be administered after resolution of symptoms. The Investigator should discuss with the Sponsor's Medical Monitor if the SAR444245 infusion needs to be delayed more than 1 day.

Guidelines for the management of SAR444245 IRR events are provided in [Table 4](#). Participants who develop Grade 2 IRR should have the next SAR444245 infusion given at half the infusion rate. For instructions on premedication at subsequent dosing, please see Section 6.1.2.1 of the master protocol.

Table 3 - Pembrolizumab infusion-related reaction dose modification and treatment guidelines

NCI CTCAE Grade	Treatment	Premedication at subsequent dosing
Grade 1 Mild transient reaction; infusion interruption not indicated; intervention not indicated	
• Increase monitoring of vital signs as medically indicated until the participant is deemed medically stable in the opinion of the investigator.	None

NCI CTCAE Grade	Treatment	Premedication at subsequent dosing
Grade 2 Requires therapy or infusion interruption but responds promptly to symptomatic treatment (eg, antihistamines, NSAIDs, narcotics, IV fluids); prophylactic medications indicated for ≤24 hrs.	
 Stop Infusion. Additional appropriate medical therapy may include but is not limited to: 
 - IV fluids, - Antihistamines, - NSAIDs, - Acetaminophen, - Narcotics. Increase monitoring of vital signs as medically indicated until the participant is deemed medically stable in the opinion of the investigator. If symptoms resolve within 1 hour of stopping drug infusion, the infusion may be restarted at 50% of the original infusion rate (eg, from 100 mL/hr. to 50 mL/hr.). Otherwise, dosing will be held until symptoms resolve and the participant should be premedicated for the next scheduled dose. 	Participant may be premedicated 1.5 h (±30 minutes) prior to infusion of pembrolizumab with: Diphenhydramine 50 mg po (or equivalent dose of antihistamine). Acetaminophen 500-1000 mg po (or equivalent dose of analgesic).
Participants who develop Grade 2 toxicity despite adequate premedication should be permanently discontinued from further study drug treatment		
Grades 3 or 4		No subsequent dosing
Grade 3: Prolonged (ie, not rapidly responsive to symptomatic medication and/or brief interruption of infusion); recurrence of symptoms following initial improvement; hospitalization indicated for other clinical sequelae (eg, renal impairment, pulmonary infiltrates)	
 Stop Infusion. Additional appropriate medical therapy may include but is not limited to: 
 - Epinephrine*, - IV fluids, - Antihistamines, - NSAIDs, - Acetaminophen, - Narcotics, - Oxygen, - Pressors, - Corticosteroids. 	
Grade 4: Life-threatening; pressor or ventilator support indicated	
 Increase monitoring of vital signs as medically indicated until the participant is deemed medically stable in the opinion of the investigator. Hospitalization may be indicated. 	
*In cases of anaphylaxis, epinephrine should be used immediately. Participant is permanently discontinued from further study drug treatment.		

Appropriate resuscitation equipment should be available at the bedside and a physician readily available during the period of drug administration. For further information, please refer to the Common Terminology Criteria for Adverse Events v5.0 (CTCAE) at <http://ctep.cancer.gov>.

Table 4 - SAR444245 Infusion-related reaction dose modification and treatment guidelines

NCI CTCAE Grade	Treatment
Grade 1 Mild transient reaction; infusion interruption not indicated; intervention not indicated	If IRR happens during infusion, continuation of SAR444245 ^a infusion is per Investigator's judgment following close direct monitoring of the participant's clinical status. SAR444245 infusion may be interrupted at any time if deemed necessary. If interrupted, IRR will be classified as Grade 2 as per NCI-CTCAE definition. If IRR happens after completion of infusion, increase monitoring of vital signs as medically indicated until the participant is deemed medically stable in the opinion of the investigator.
Grade 2 Requires therapy or infusion interruption but responds promptly to symptomatic treatment (eg, antihistamines, NSAIDs, narcotics, IV fluids); prophylactic medications indicated for ≤24 hrs.	SAR444245 infusion should be interrupted if applicable. If symptoms resolve within 1 hour of interrupting drug infusion, the infusion may be restarted at 50% of the original infusion rate. Otherwise, dosing will be held until symptoms resolve and the participant should be premedicated for the next scheduled dose according to Section 6.1.2.1 of the master protocol. The next infusion should be given at half the infusion rate. During or after completion of infusion, additional appropriate medical therapy may include but not limited to IV fluids, antihistamines, NSAIDs, acetaminophen, narcotics. Increase monitoring of vital signs will be as medically indicated until the participant recovers.
Grade 3 Prolonged (ie, not rapidly responsive to symptomatic medication and/or brief interruption of infusion); recurrence of symptoms following initial improvement; hospitalization indicated for other clinical sequelae	SAR444245 infusion should be interrupted if applicable. If IRR is clearly attributable to SAR444245, SAR444245 should be permanently discontinued. The participant can continue treatment with the other anti-cancer therapy in combination During or after completion of infusion, additional appropriate medical therapy may include but is not limited to epinephrine ^b , IV fluids, antihistamines, NSAIDs, acetaminophen, narcotics, oxygen, vasopressors, corticosteroids. Increase monitoring of vital signs as medically indicated until the participant recovers.
Grade 4 Life-threatening; pressor or ventilator support indicated	SAR444245 infusion should be interrupted if applicable. If IRR is clearly attributable to SAR444245, SAR444245 should be permanently discontinued. The participant can continue treatment with the other anti-cancer therapy in combination During or after completion of infusion, additional appropriate medical therapy may include but is not limited to epinephrine ^b , IV fluids, antihistamines, NSAIDs, acetaminophen, narcotics, oxygen, vasopressors, corticosteroids. Increase monitoring of vital signs as medically indicated until the participant recovers.

^a Information for preparation and storage of SAR444245 are provided in the pharmacy manual.

^b In cases of anaphylaxis, epinephrine should be used immediately

Abbreviations: CTCAE = Common terminology criteria for adverse events; IRR = Infusion-related reaction; NCI = National Cancer Institute; NSAIDs: nonsteroidal anti-inflammatory drugs.

6.5.4.2 *Anaphylaxis*

Anaphylaxis should lead to immediate interruption of ongoing infusion, and to permanent discontinuation of both SAR444245 and pembrolizumab being administered.

Management should be prompt and may include but is not limited to administration of epinephrine, IV fluids, antihistamines, oxygen, vasoressors, corticosteroids, as well as increased monitoring of vital signs as medically indicated, until the participant recovers (see guidelines) (37, 38, 39).

6.5.4.3 *Fever, flu-like symptoms and cytokine-release syndrome (CRS)*

Fever can frequently happen with infusion of IL-2 and may possibly evolve into flu-like symptoms or could be an early manifestation of CRS. Fever or flu-like symptoms should be graded according to CTCAE V5.0 and managed according to institutional standards.

Cytokine-release syndrome should be graded as per American Society for Transplantation and Cellular Therapy (ASTCT) criteria integrated with central laboratory cytokine results, and managed per guidelines in [Table 5](#). If any grade of CRS is suspected, sites should make every effort to draw an additional blood sample for cytokines levels (by central laboratory) prior to the administration of tocilizumab, as well as C-reactive protein (CRP) and ferritin (by local laboratory).

Sites should have at least 2 full doses of tocilizumab available and access to an intensive care unit (ICU), in case participants develop CRS.

Guidelines for management of CRS according to severity grading are provided in [Table 5](#). ASTCT CRS consensus grading scale is provided in Section 10.11 of the master protocol.

Table 5 - Guidelines for the management of suspected cytokine release syndrome (CRS)

Event severity (ASTCT CRS Consensus Grading)	Recommended SAR444245 dose modification and supportive care guidelines
Grade 1 
• Fever (Temperature $\geq 38^{\circ}\text{C}$)^b• No hypotension• No hypoxia	No dose modification of SAR444245^a Appropriate symptomatic treatment may include but is not limited to IV fluids (care should be taken to not excessively hydrate if evidence of vascular leak), antihistamines, NSAIDs and acetaminophen. Close direct monitoring of the participant's clinical status. Clinical and laboratory monitoring should initially be performed daily, then less frequently as the participant improves.
Grade 2 
• Fever^b (Temperature $\geq 38^{\circ}\text{C}$)• Hypotension not requiring vasoressors• and/or^c hypoxia requiring low-flow nasal cannula^d or blow-by.	Temporarily interrupt SAR444245 if event occurs during infusion Additional appropriate medical therapy may include but is not limited to IV fluids (care should be taken to not excessively hydrate if evidence of vascular leak), antihistamines, NSAIDs and acetaminophen. Monitoring of vital signs, cardiac and other organ functions closely as medically indicated should be increased until the participant recovers. Transfer to ICU may be required. For participants with comorbidities, older age, or with oxygen requirement,

Event severity (ASTCT CRS Consensus Grading)	Recommended SAR444245 dose modification and supportive care guidelines
Grade 3	
hypotension, or participants in whom symptoms (eg, high grade fever) that do not respond to antipyretics within 72 hours treatment with corticosteroids and/or tocilizumab should be considered, as per guidance for Grade 3 events.
 
SAR444245 may be resumed when clinical symptoms have resolved or improved to Grade 1 and corticosteroid taper. No dose modification is required but decreasing to half the infusion rate can be considered.

Grade 4	
If CRS grade 3, SAR444245 should be temporarily cycle delayed, and subsequent treatment should be resumed only when symptoms have resolved or improved to Grade 1 at █ µg/kg or permanently discontinued, as clinically indicated.
 
If CRS Grade 4, SAR444245 should be permanently discontinued as clinically indicated.
 
If CRS Grade 3 or Grade 4, IV corticosteroids should be initiated (outside of the context of CAR-T cells, corticosteroids alone maybe initiated in first intention) and tocilizumab considered, and/or epinephrine and/or other vasopressors should be administered as needed. Participants with severe CRS may require management in intensive care setting, with monitoring of clinical status and laboratory tests performed at least daily.
 
As the participant improves, the intensity of the monitoring and setting can be decreased, but the participant should not be discharged from the hospital until clinically stable. Corticosteroids can then be administered IV or orally every 8 hours for up to 3 days, then tapered over 4 days. In general, tapering of steroids can start when vasopressors and high-flow oxygen are no longer needed.
 
CRS is considered resolved when there is sustained resolution of fever and there is no longer a need for oxygen supplementation to relieve hypoxia nor vasopressors to maintain blood pressure; however, normalization of temperature alone does not define resolution of CRS.

	
If no clinical improvement in oxygenation, hypotension, fever, and other CRS manifestations is observed within 24 to 72 hours, management for persistent or worsening CRS should be initiated. Re-evaluation for other contributing conditions should be done, such as infection, cardiac, thromboembolic and other complications. Intravenous Tocilizumab at 8 mg/kg (for participants weighing ≥ 30 kg) should be administered, and steroids should be administered concurrently. If still no improvement in oxygenation, hypotension, fever and other manifestations is observed after the first dose of tocilizumab, it may be repeated after an interval of at least 8 hours and should not exceed 4 doses in total.
 
For participants with severe CRS who fail to improve after repetitive treatment with both tocilizumab and steroids, alternative options should be discussed with clinical site specialists

a Information for preparation and storage of SAR444245 is provided in the pharmacy manual.

b Fever is defined as temperature $\geq 38^{\circ}\text{C}$ not attributable to any other cause. In patients who have CRS then receive antipyretic or anticytokine therapy such as tocilizumab or steroids, fever is no longer required to grade subsequent CRS severity. In this case, CRS grading is driven by hypotension and/or hypoxia.

c CRS grade is determined by the more severe event: hypotension or hypoxia not attributable to any other cause. For example, a patient with temperature of 39.5°C , hypotension requiring 1 vasopressor, and hypoxia requiring low-flow nasal cannula is classified as Grade 3 CRS.

d Low-flow nasal cannula is defined as oxygen delivered at ≤ 6 L/minute. Low flow also includes blow-by oxygen delivery, sometimes used in pediatrics. High-flow nasal cannula is defined as oxygen delivered at > 6 L/minute.

Abbreviations: AE = Adverse event; ASTCT=American Society for Transplantation and Cellular Therapy; BiPAP= Bilevel Positive Airway Pressure; CPAP= Continuous Positive Airway Pressure; CRS= cytokine release syndrome; ICU=intensive care unit; IL = Interleukin; IMP=investigational medicinal product; IV = Intravenous; NSAIDs=Non-steroidal anti-inflammatory drugs.

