6.5 DOSE MODIFICATION

6.5.1 General rules

Dose modifications for SAR444245 are permitted according to the guidelines described in this section. Pembrolizumab dose reductions are not permitted. Pembrolizumab treatment may be interrupted or discontinued due to toxicity.

Dose modifications different from those stated in the protocol should only be made in consultation with the Sponsor, unless required for immediate participant safety.

Cycle delay (ie, Day 1 should be delayed for all IMPs) is permitted in case of treatment-emergent adverse event (TEAE). Dose modification will be made according to the worst grade of toxicity observed within a cycle. If a participant experiences several toxicities and there are conflicting recommendations, the most conservative recommended dose adjustment should be followed.

In participants who have SAR444245 dose reduction due to SAR444245 related Grade ≥ 3 treatment-related adverse events (TRAEs), SAR444245 dose may be re-escalated to █ $\mu\text{g}/\text{kg}$ if:

- no SAR444245 related Grade ≥ 3 TRAE or clinically significant laboratory abnormality within at least 2 subsequent cycles, AND
- both Investigator and Sponsor agree that the participant has clinical benefit.

Administration of the study treatment will be discontinued in the event of a TEAE that persists despite appropriate dose modifications or any other TEAE that, in the opinion of the Investigator, warrants discontinuation.

If any of the IMP components is permanently discontinued, the other IMP component can be continued until disease progression or other criteria as detailed in Section 7.1.1 of the master protocol are met. In this case, it is partial permanent discontinuation, and the end of treatment (EOT) assessment will be 30 days after the date of the last administration of the remaining IMP. When all IMP components are permanently discontinued, it is full permanent discontinuation.

All changes to study treatment administration must be recorded in the electronic case report form (e-CRF).

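### Substudy 01 gives contradictory stopping rules for anaphylaxis, and Table 3 does not say which agent its term study drug covers

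*Protocol*

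**What the plan says.** All the rules at issue are in Substudy 01, section 6.5.

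- **6.5.4.1, body text.** An infusion-related reaction is defined by timing alone: during the infusion or within 24 hours of its completion. Anaphylaxis is named among the reactions that pembrolizumab may cause. After a Grade 3 or 4 pembrolizumab reaction, "the SAR444245 infusion will be delayed and can be administered after resolution of symptoms". The Sponsor's medical monitor is consulted if the delay needs to exceed 1 day.
- **Table 3, pembrolizumab reactions, Grades 3 or 4.** The premedication column reads "No subsequent dosing". Next to the note on epinephrine for anaphylaxis stands: "Participant is permanently discontinued from further study drug treatment".
- **Table 4, SAR444245 reactions, Grades 3 and 4.** "If IRR is clearly attributable to SAR444245, SAR444245 should be permanently discontinued. The participant can continue treatment with the other anti-cancer therapy in combination". A footnote to epinephrine says to use it at once in anaphylaxis.
- **6.5.4.2, Anaphylaxis.** The ongoing infusion is interrupted, followed by "permanent discontinuation of both SAR444245 and pembrolizumab being administered".
- **6.5.1, General rules.** Stopping one agent is a planned option: "If any of the IMP components is permanently discontinued, the other IMP component can be continued until disease progression", subject also to the other stopping criteria. This is partial permanent discontinuation. Stopping all components is full permanent discontinuation.

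**The concern.** An investigator managing anaphylaxis can find two instructions that cannot both be followed. One allows the other agent to be given or continued, and the other ends both agents permanently. Which one is applied depends on the paragraph the site reads, at a moment of high risk to the participant.

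The choice also reaches the safety data. Master protocol section 9.4.3.5 counts adverse events leading to partial and to full permanent discontinuation as separate outputs. Substudy section 6.5.1 times the end-of-treatment assessment from the last dose of the remaining agent, and master protocol section 9.4.1 closes the on-treatment period 30 days after the last administration of investigational product. Two participants with the same event could therefore have different discontinuation categories and observation windows because their sites followed different paragraphs.

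**Working it through.** No sample size, rate or error probability is involved, so the check is a comparison of the passages, case by case. The first question is whether anaphylaxis falls inside the infusion-reaction rules. It does: the definition in 6.5.4.1 is purely temporal, the same section names anaphylaxis as a pembrolizumab reaction, and neither the body text nor Table 4 carves it out of the Grade 3 and 4 rules.

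| Event (Grade 3 or 4) | Rules that apply | Result |
|---|---|---|
| Anaphylaxis due to pembrolizumab | 6.5.4.1 text: SAR444245 may be given after resolution. 6.5.4.2: both agents stop permanently. | Direct contradiction |
| Anaphylaxis due to SAR444245 | Table 4: SAR444245 stops, the other agent can continue. 6.5.4.2: both agents stop permanently. | Contradiction, because Table 4 has no exception |
| Pembrolizumab reaction, not anaphylaxis | 6.5.4.1 text: SAR444245 may be given after resolution. Table 3: study drug stops permanently. | Ambiguous |
| Reaction clearly attributable to SAR444245, not anaphylaxis | Table 4 only | No conflict |

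The third row turns on one term. If study drug in Table 3 means pembrolizumab, the table agrees with the body text and the outcome is partial discontinuation under 6.5.1. If it means both agents, the table contradicts the body text. Usage elsewhere does not settle the matter. Section 6.5.4.4 uses a plural covering all study drugs when it means both, and a footnote to Table 6 refers to full study treatment. This leans towards the narrow reading of Table 3 but does not define the term.

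The next question is whether another passage resolves the conflict. Section 6.5.1 tells sites to take the most conservative dose adjustment, but that sentence is written for a participant with several toxicities and conflicting recommendations. Here there is one toxicity under two rules, so it does not clearly apply. Section 6.5.3 leaves the final decision on dose modification to the investigator's judgment, which permits variation between sites and does not rank the rules. There is no cross-reference between 6.5.4.1 and 6.5.4.2.

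**The case against.** The best defence is that the rules have different triggers and that anaphylaxis has its own section. The body text of 6.5.4.1 and Table 3 deal with pembrolizumab reactions, Table 4 with SAR444245 reactions, and 6.5.4.2 with anaphylaxis alone. The last follows the tables directly and names both agents, so on an ordinary reading the specific section governs the general one. The Table 4 footnote is a treatment note attached to epinephrine and does not itself say that the other agent may continue after anaphylaxis.

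Much of this stands. A reader might infer that the substudy gives opposite answers for every severe infusion reaction. The documents do not support that, as the last two rows of the comparison show. A reader might also cite the Grade 3 infusion reaction reported as dose-limiting in master protocol section 4.3 as an instance of the conflict. It occurred on SAR444245 monotherapy and is not described as anaphylaxis. Nor does 6.5.4.1 call for giving the causative drug again, or for dosing on the same day. It permits the other agent after symptoms resolve.

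On the data, the on-treatment period follows actual administrations and treatment changes are recorded in the case report form. The tables would therefore report what was done. The problem is variation in practice, not misclassification.

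The defence does not remove the anaphylaxis conflict. Giving precedence to 6.5.4.2 is a reasonable inference that the protocol never states, and a site working from 6.5.4.1 or a table is not directed there.

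**Conclusion.** The point holds in limited form. Substudy 01 contradicts itself on anaphylaxis: squarely when pembrolizumab is the cause, and through the absence of an exception in Table 4 when SAR444245 is the cause. The undefined term in Table 3 is a further ambiguity, which becomes a contradiction only if it means both agents.

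The frequency of such events cannot be derived from the documents. It is probably low: the risk table in master protocol section 10.10 reports no anaphylaxis in the first-in-human study at the time of writing. The objective response rate, its confidence interval and the planned sample size do not change. The weight of the point lies in participant safety after a potentially life-threatening event and in site-dependent partial or full discontinuation. The conclusion assumes that anaphylaxis is handled as an infusion reaction, as the definition in 6.5.4.1 implies. It makes no judgment on which clinical rule is right.

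**What to change.** The sponsor should reconcile the body text of 6.5.4.1, Tables 3 and 4, and 6.5.4.2, and then:

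1. State which passage governs anaphylaxis, and cross-refer to it from 6.5.4.1 and both tables.
2. Replace study drug in Table 3 with the named component or components.
3. For each situation, give the outcome as partial or full permanent discontinuation in the sense of 6.5.1, so that it maps directly to the safety tables.

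Any other substudy that repeats these sections needs the same check. The contents list of Substudy 02 shows the same section and table titles, but its text on this point was not available. The choice of clinical rule rests with the sponsor. The cost is a wording change in an amendment, with no new procedure or assessment.
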